1. TITLE

Post-Operative Urinary Retention (POUR) in Thoracic Surgery Patients Receiving Prophylactic Tamsulosin

2. EXTERNAL IRB REVIEW HISTORY*

NA

3. PRIOR APPROVALS:

NA

Conflict of Interest (COI): The investigators have nothing to disclose

Biohazardous Agents: NA

Radiation: NA

4. OBJECTIVES*

Post-Operative Urinary Retention (POUR) in Thoracic Surgery is a prospective interventional study aiming to test the hypothesis that the prophylactic use of tamsulosin prior to thoracic surgery in high-risk patients leads to reduced rates of POUR. Urinary retention is defined as eight hours without void after Foley catheter removal and symptoms or bladder volume greater than 600cc.

5. BACKGROUND*

Post-operative urinary retention (POUR) is one of the most common post-operative complications encountered by most surgical specialties. The incidence of POUR can vary from five to 70%.¹ POUR associated factors reported in the literature include type of anesthesia, type and duration of surgery, underlying comorbidities, as well as medicines used in perioperative period. The development of POUR can increase the length of hospitalization and lead to significant morbidities such urinary tract infection, detrusor muscle dysfunction, delirium, cardiac arrhythmias among others.¹

INVESTIGATOR STUDY PLAN

POUR definition in the literature is not homogeneous, and include >200mL by bladder scanner 4 hours post-op, >500mL by bladder scanner 8 hours post-catheter removal, and >600mL by bladder scanner 4 hours after removal of indwelling urinary catheter.²⁻⁴ Urinary retention is defined in the current study as eight hours without void after Foley catheter removal and symptoms or bladder volume greater than 600 cc.

There are a limited number of studies available regarding POUR after thoracic surgery, and among those, the results vary. In addition, there is continued discussion regarding the appropriate time to remove a urinary catheter post-op to prevent or reduce POUR. Early removal increases the risk for urinary retention, but late removal increases the risk for acquiring a catheter-related UTI⁵. Although it is currently mandated to remove the urinary catheter 48 hours post-op, studies have looked at whether they can be removed earlier without increasing the risk for catheterization. Results of the current published studies are conflicting. Chia, et al compared patients who underwent transurethral catheter removal on the first post-op day with those who had removal after discontinuing patient-controlled epidural anesthesia, usually on the third post-op day. Patients in both groups did not require re-catheterization for retention or suffer from catheter-associated UTIs. However, not surprisingly, catheter-induced urethral pain was higher in the group that underwent later removal. The authors therefore concluded that removal of bladder catheter as early as post-op day one is preferable due to no difference in UTIs or re-catheterization as well as decreased urethral pain (2009)⁶. Other studies noted that earlier removal did not increase the risk for POUR and subsequent re-catheterization⁰ but was associated with decreased risk for UTIs (4,2). On the contrary, Zaouter, et al defined a correlation between early removal and increased POUR and re-catheterization⁷.

The role of prophylactic tamsulosin administration in prevention of POUR has been investigated across various surgical subspecialties. Results of these studies are also mixed. In patients undergoing urologic procedures including varicocelectomy, inguinal herniorrhaphy, and scrotal surgery, POUR was significantly lower in the group who received tamsulosin (5.9%) compared to the placebo group (21.2%)⁸. However, there was no difference in POUR rates in patients who underwent spinal surgery or colorectal surgery^{9,10}.

Although there are varying data across studies measuring POUR after thoracic surgery, there are several risk factors that have consistently been identified that predispose patients to increased risk of POUR after thoracic surgery: age above 40 years, male, diabetes, and BPH¹¹.

INVESTIGATOR STUDY PLAN

The age cutoff is debatable, but in general, it is accepted that older age correlates with numerous types of bladder dysfunction ⁶. There are also certain procedures within thoracic surgery that increase the risk. Lung resection surgery resulted in the highest rate of POUR compared to other procedures like sympatheticotomies, pleural biopsies, and mediastinal procedures ¹. In a review of all UMass Memorial patients who underwent thoracic surgery in 2019, the group with the highest incidence of POUR consisted of males above the age of 60 who underwent major thoracic resections. The rate in this cohort was as high as 21%. Although tamsulosin was designed and used to treat patients with symptomatic BPH, we would like to study the effect of prophylactic tamsulosin in the group of patients with the highest likelihood to develop POUR in an effort to prevent this complication.

Post-operative urinary retention is a prevalent complication. Patients who undergo thoracic surgery have greater urinary retention rates compared to others. Data on effective methods to reduce the risk of POUR in this high-risk group are limited.

6. INCLUSION AND EXCLUSION CRITERIA*

Inclusion criteria:

- All male patients ≥ 60 years old undergoing inpatient thoracic surgery for major resections.

Exclusion criteria:

- Prisoners
- Adults unable to consent
- End stage renal disease on hemodialysis
- Indwelling urinary catheter
- Child-Pugh class C hepatic failure
- Usage of the following medications prior to surgery: strong CYP 3A4 inhibitors, other alpha-adrenergic blocking agents.

INVESTIGATOR STUDY PLAN

- patients known to be CYP2D6 poor metabolizers
- History of prostatectomy or cystectomy
- Patients with contraindications to tamsulosin and those at high risk for side effects: hypersensitivity to tamsulosin HCl or any component of FLOMAX capsules,⁵ hypersensitivity to sulfonamides. History of known glaucoma, hypotension, plan to undergo cataract surgery in the next 2 weeks

7. STUDY-WIDE NUMBER OF SUBJECTS*

NA

8. STUDY-WIDE RECRUITMENT METHODS*

NA

9. STUDY TIMELINES*

The study will be conducted for twenty-four months from July 2021 – December 2023. The study subjects will be enrolled on an ongoing basis and will include all that fulfill the eligibility criteria.

10. STUDY ENDPOINTS*

See #4

11. PROCEDURES INVOLVED*

There will be no randomization process as this is a single arm trial. The patients will first provide consent to the research when they visit the clinic or in an inpatient setting. As part of the screening process, a physician (or physician's assistant or nurse practitioner) will review the patient's medication list for potential drug-drug interactions with tamsulosin, make a clinical decision regarding the safety of study participation, and document that this screening has occurred.

INVESTIGATOR STUDY PLAN

Since visits are being done remotely, study medication will be mailed to the subject's home and a study staff member will call to answer any questions they may have on how to take the medication. Otherwise, the medications will be dispensed in person by IDS to a research coordinator. The research coordinator will then give the medication to the patient at the time of their Pre-surgical evaluation at the Memorial campus anesthesia clinic.

Starting 2 days before surgery, patients will receive 0.4 mg Tamsulosin nightly, then on the day of surgery, 0.4 mg in holding area, and any additional consecutive days if they experience retention, which is the standard of care for all patients that present with POUR. The minimum number of days a subject could be on the study drug is 3. Tamsulosin is FDA approved and is predominantly used to treat the signs and symptoms of benign prostatic hyperplasia.

The data collection includes identification of patient and operation characteristics that correlate with development of POUR. Some of the factors we propose to study include age, operating time, type of surgery, indication for surgery, presence of epidural, development of other postoperative complications. Patients' names will be de-identified with a unique identifier and will be paired with the corresponding MRN. Principal Investigator and research coordinator will have access to those identifiers.

12. DATA AND SPECIMEN BANKING*

NA

13. DATA ANALYSIS AND MANAGEMENT *

Hypothesis: Prophylactic tamsulosin decreases the rate of postoperative urinary retention (POUR) rates in patients undergoing thoracic surgery

- Primary aim: compare the rates of POUR in thoracic surgery patients treated with preop tamsulosin with historic controls.

INVESTIGATOR STUDY PLAN

The rates of POUR for major procedures in UMass Thoracic service in the target population (male over 60 years old) varied from 8.3% to 33.3% over the last 5 years. In the overall thoracic population, this number was in average 8.4% and it varied from 4.3% to 9.3%.

When analyzing all major procedures performed in the 2019, 48 were performed in males over 60 years old, the study target population. The POUR rate was 33.3%. After applying the exclusion criteria on those 48 individuals, we found an exclusion rate of 33.3% where 16 individuals were excluded, 8 for using Flomax prior to surgery and 8 for using one of the following medications: Bupropion Fluconazole, TMP-SMX, Silodosin, Paroxetine Terazosin, Levofloxacin, Prazosin, Fluoxetine, Sildenafil.

The overall POUR rate was 33% and among the 32 eligible individuals, POUR rate was 28%.

Power Calculation

The incidence rate of 28% was used to estimate the possible scenarios of sample and power of analysis presented in **Error! Reference source not found.**

The number needed to treat is 60 assuming an 80% reduction of POUR with a power of 80%. Assuming the same volume of operations and taking into account the number excluded due to exclusion criteria (33%), and refusal rate of 25%, we expect to accrue 24 patients per year and achieve the number needed to treat (n=60) in 2.5 years.

All patients who fulfill the eligibility criteria and thus may benefit from the intervention (use of Tamsulosin pre-operatively) will be invited to participate in the study. **(Error! Reference source not found.)**

Table 1. Sample calculation and power-analysis in three hypothetical scenarios of varying effects of tamsulosin

	Hypothetical POUR Incidence in Intervention Group (%)	N*	Post-hoc Power estimate (I)
Tamsulosin intervention Group effect 1 (reduction of 50%)	14	150	49.3%
Tamsulosin intervention Group effect 2 (reduction of 80%)	5.6	60	80.4%
Tamsulosin intervention Group effect 3 (reduction of 90%)	2.8	32	80.4%

*N of male over 60 years old that undergo to in-patient procedures (I) <https://clincalc.com/stats/SampleSize.aspx>

INVESTIGATOR STUDY PLAN

(II) <https://jongguri.shinyapps.io/samplepower/>

The study selected parameters are:

- Incidence, group historical control 2019 – 28%
- Incidence (expected), intervention with Tamsulosin – 5.6% (reduction of 80% in incidence)
- Subjects, group control – 32 individuals
- Subjects, group intervention (expected) -60 individuals
- Alpha - 0.05

It is expected that the population undergoing thoracic services are similar over time and it will be appropriate to use historical controls to compare with the intervention group.

Our analytical plan is to test the proportion of POUR within the study population comparing with the historical controls. The data quality will be monitored by monthly verification of the completeness of the data, missing values and accurateness of the variables collected.

If a statistically significant reduction in POUR rates is observed before the end of the study, the study will stop and Tamsulosin will be adopted as prophylaxis for this high-risk population in thoracic surgery division. If the benefit is not observed with the estimated sample, the study will be reassessed.

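### The only control year named, 2019, is by section 13 the top of the target population's five-year POUR range before exclusions, and the plan does not show that its eligible-only rate of 28% is representative

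*Combined protocol and SAP*

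**What the plan says.** The trial is single-arm, and its primary aim is to "compare the rates of POUR in thoracic surgery patients treated with preop tamsulosin with historic controls". All of the following is in section 13 unless stated.

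- **Five-year range.** In the target population, before exclusions, the rate "varied from 8.3% to 33.3% over the last 5 years".
- **2019 before exclusions.** Of the major procedures that year, "48 were performed in males over 60 years old, the study target population. The POUR rate was 33.3" per cent.
- **2019 after exclusions.** "The overall POUR rate was 33% and among the 32 eligible individuals, POUR rate was 28" per cent.
- **Control group.** The selected parameters list "Incidence, group historical control 2019" at 28%, with 32 control and 60 treated men, an expected treated rate of 5.6% and alpha 0.05. No other year is named.
- **Justification.** "It is expected that the population undergoing thoracic services are similar over time".
- **Analysis.** "Our analytical plan is to test the proportion of POUR within the study population comparing with the historical controls". Neither the years nor the test is stated.
- **Consequence.** If a significant reduction is seen before the end, "the study will stop and Tamsulosin will be adopted as prophylaxis for this high-risk population".
- **Section 5 (Background).** A 2019 review is cited with a rate of up to 21% in men above 60 having major resections, apparently the same group.

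**The concern.** With no concurrent control, the inference rests on how well the historical rate stands for what enrolled men would have experienced without tamsulosin. The one year named has, by section 13, the highest pre-exclusion rate of five, and the lowest is a quarter of it. That spread does not support the expectation of similarity over time. If 28% was also high among eligible men and the no-drug rate during enrolment is clearly lower, part or all of an observed reduction would be the return to a more usual rate. The plan would credit it to the drug, and a significant result leads to adoption as routine prophylaxis.

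**Working it through.** **Inputs.** From section 13: range 8.3% to 33.3%; 2019 33.3% of 48 and 28% of 32; 60 treated; expected 5.6%; alpha 0.05. Assumed: two-sided test, one final analysis. The test is not named, so results are given as Fisher exact / chi-square without continuity correction.

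**1. Counts behind the rates.** 33.3% × 48 = 16 events. 28% × 32 ≈ 9 events (9/32 = 28.1%). Range: 33.3/8.3 = 4.0-fold.

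**2. The plan's own power (stated 80.4%).** Normal approximation with pooled variance under the null:
- pooled rate = (32×0.28 + 60×0.056)/92 = 0.1339
- SE under the null = √[0.1339×0.8661×(1/32+1/60)] = 0.0745
- SE under the alternative = √[0.28×0.72/32 + 0.056×0.944/60] = 0.0847
- power = Φ[(0.224 − 1.96×0.0745)/0.0847] = 82.1%

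Exact Fisher power is 80.5%. The stated figure is reproduced, so the numbers below use the plan's own design.

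**3. What counts as success against 9/32.**

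| Treated events | Fisher p | Chi-square p |
|---|---|---|
| 6/60 | 0.037 | 0.025 |
| 7/60 | 0.080 | 0.047 |
| 8/60 | 0.097 | 0.082 |

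Success needs at most 6 events (Fisher) or 7 (chi-square).

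**4. Chance of success with an inert drug.** Let X be the treated events, binomial with n = 60 and true no-drug rate p. The chance is P(X ≤ 6) / P(X ≤ 7).

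| True no-drug rate | Fisher | Chi-square |
|---|---|---|
| 28% | 0.06% | 0.2% |
| 25% | 0.3% | 0.9% |
| 21% | 2.0% | 4.6% |
| 18% | 6.7% | 13.1% |
| 15% | 18.5% | 30.5% |

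These are conditional on the control result 9/32. If controls and treated both vary at a common 28%, the chance of a false benefit is 2.1%/2.6%. The table should therefore not be judged against a 2.5% error limit.

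**5. Section 5 against section 13.** 21% of 48 is about 10 events (10/48 = 20.8%), against 16. Ten events would be compatible with 9/32 if one of the 16 excluded men had POUR. So 21% conflicts with 33.3%, but not necessarily with 28%.

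**6. What pooling would do.** Assume five years of 32 eligible men, 160 controls, with control and treated counts both random.

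| Controls | Rate in treated men | Chance of success (Fisher/chi-square) |
|---|---|---|
| Plan: 32 at 28% | 5.6% | 80%/85% |
| Pooled: 160 at 20.8% | 5.6% | 82%/85% |
| Pooled: 160 at 15% | 5.6% | 44%/48% |
| Pooled: 160 at 20.8%, inert drug | 15% | 13%/15% |

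The 20.8% is only the midpoint, (8.3 + 33.3)/2. In the second and third rows the current no-drug rate is taken as 28% with a true 80% reduction.

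**The case against.** The strongest reply is that no typical rate is known. The plan gives the extremes only. At 21% the chance of a false benefit is small, and at 25% or 28% it is negligible. Enrolment is expected to take 2.5 years, so a single low year would not decide the result. The one multi-year average in section 13, 8.4% in a range of 4.3% to 9.3% for all thoracic patients, lies near the top of its range. That is a different population, but it does not suggest that usual years lie far below the maximum. All of this stands and limits how strongly the point can be put.

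The range and the comparator are also on different bases. The excluded men had about 7 events in 16 (16 − 9 of 48 − 32), or 44%, so changes in the share excluded could explain part of the spread. This stands too, but it is equally a reason to ask for yearly eligible-only counts.

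The 2019 line is one of the design parameters, and the analysis sentence speaks only of historical controls. The 2019-only comparison is the natural reading, not a stated rule. On either reading the control years need to be named.

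A reader might infer three stronger things that the documents do not support:

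- **That 28% is the peak among eligible men.** No other eligible-only rate is given.
- **That the bottom of the range applies.** At 8.3% the chance of false success would be 77%/88%, but that is a pre-exclusion extreme which would have to persist throughout enrolment.
- **That 2019 was a chance high that must fall back.** With 48 men a year and a constant 20% rate (assumed), a simulated five-year spread of 25 points or more has a chance of only 2.6%. Rates may really have changed, and the order of the years is not given. If they rose, 2019 may be the better guide and pooling would work against the drug.

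**Conclusion.** The concern holds in a limited form and should be fixed, with medium confidence. By section 13, the only named control year is the highest of five before exclusions. The plan neither shows that its eligible-only rate is representative nor supports the stability on which the comparison depends. The consequence ranges from negligible (no-drug rate of 25% or more) through modest (about 21%) to serious (18% or lower), and the plan cannot place the trial within that range. The figures assume 9/32 controls, 60 treated men, one final two-sided test at 0.05 and no drug effect. They do not show that the trial's type I error is inflated. The peak premise itself depends on 33.3% being right: if the 21% in section 5 is correct for the same men, 2019 is not the peak, although the need to name and justify the control years remains.

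**What to change.** 1. Reconcile the 21% in section 5 with the 33.3% in section 13 for 2019.
2. Apply the trial's eligibility criteria and POUR definition to all five years, and report eligible men and POUR events for each year.
3. Before any comparison with treated patients, state the control years in section 13. Make the pooled multi-year group primary, with 2019 alone as a sensitivity analysis, unless the yearly eligible rates show a clear trend or a change in recording. In that case, justify the years chosen and report the other set as the sensitivity analysis. Name the test in the same sentence.
4. Restate the planning rate and power from the chosen control group's actual rate and size.

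**Cost.** Chart screening of four more years, for a population in which the service already has POUR rates, and new wording in section 13. No extra trial patients are needed. Older years may differ in practice or recording, and the control rate is likely to be less favourable: if the pooled rate is 15% while the current rate is 28%, the chance of success falls to about 44%/48%. Pooling reduces the dependence on one year but does not remove historical-control bias, as the 13%/15% in the last row of step 6 shows.

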25. LOCAL NUMBER OF SUBJECTS

Considering the volume of procedures in 2019 of 48 procedures is maintained over time, it is estimated that we will be able to enroll 60 patients within 2.5 years. This sample size would allow detection of 80% reduction in POUR with a power of 80%. This number of subjects considers a refusal rate of 25% and exclusion rate of 33%.

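### Eight of the 48 men from 2019 were removed under a ten-drug list that does not match the section 6 medication criterion, so the treated group and its only comparator are not assured of the same selection

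*Combined protocol and SAP*

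**What the plan says.** Section 13 starts from 48 major procedures in 2019 in men over 60. It states "After applying the exclusion criteria on those 48 individuals" and reports 16 removals: 8 men already on Flomax and "8 for using one of the following medications: Bupropion Fluconazole, TMP-SMX, Silodosin, Paroxetine Terazosin, Levofloxacin, Prazosin, Fluoxetine, Sildenafil". POUR is given as 33.3% in the 48 and 28% in the 32 who remain. Those 32 men and that 28% are then the control group and control rate in the selected study parameters. The section justifies the comparison by expecting the thoracic population to be similar over time, so that "it will be appropriate to use historical controls to compare with the intervention group". The same exclusions feed enrolment in section 25: "This number of subjects considers a refusal rate of 25% and exclusion rate of 33" per cent.

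Section 6 has one criterion based on current medication: "strong CYP 3A4 inhibitors, other alpha-adrenergic blocking agents". It also excludes "patients known to be CYP2D6 poor metabolizers" and "Patients with contraindications to tamsulosin and those at high risk for side effects". The items that follow this last phrase are hypersensitivities, glaucoma, hypotension and planned cataract surgery.

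For prospective patients, section 11 adds a clinician's review of the "medication list for potential drug-drug interactions with tamsulosin, make a clinical decision regarding the safety of study participation". No drugs are named there.

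**The concern.** The trial has a single arm, so the comparison with the 2019 men is its only comparison. The least that a historical control needs is that one eligibility rule selects both groups. Here the control appears to have been selected by a named drug list, while the treated group is selected by two drug classes plus a case-by-case judgement.

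If those rules remove different men, the two groups differ before any tamsulosin is given. The control n, the 28% rate, the 33% exclusion rate, the accrual forecast and the power all come from this selection step. Section 13 would also stop the study and adopt tamsulosin on a significant reduction, so the benchmark bears directly on a change of practice.

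**Working it through.** **1. The list against section 6.** The plan assigns no drug to a class; the sorting below uses ordinary drug class and is an assumption.

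| Drugs in the section 13 list | Section 6 medication criterion |
|---|---|
| Silodosin, terazosin, prazosin | Match (alpha-blockers) |
| Fluconazole | Unclear, because section 6 says strong inhibitors |
| Paroxetine, fluoxetine, bupropion, TMP-SMX, levofloxacin, sildenafil | Match neither class |

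The other clauses do not clearly supply the missing six. Being a known CYP2D6 poor metabolizer is a patient trait, and the listed high-risk items name no interacting drug. The 8 Flomax removals are not in dispute.

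**2. Counts (section 13).** 33.3% × 48 = 16 events. 28% × 32 = 8.96, so 9 events (9/32 = 28.1%). Hence 16 − 9 = 7 events among the 16 men removed (43.8%). Fisher two-sided, 7/16 against 9/32: p = 0.34. Exact 95% CI for 9/32: 13.7% to 46.7%.

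**3. The plan's power.** Pooled normal formula, two-sided 0.05 (the plan does not state sidedness):

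power = Φ{(|p1 − p2| − 1.96·SE0)/SE1}, where SE0 uses the pooled rate and SE1 the separate rates.

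With 32 controls at 28% and 60 treated at 5.6%, the pooled rate is (32×0.28 + 60×0.056)/92 = 0.134, SE0 = 0.0745 and SE1 = 0.0847. Then (0.224 − 0.1461)/0.0847 = 0.919, and power is 82.1%. Table 1 gives 80.4%, and a Fisher exact calculation gives 80.5%. The plan's figure reproduces.

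**4. Outer limits if the list is not the rule.** Men per drug and events per drug are not given. If the list names drugs actually seen, at least one of the 8 men used an alpha-blocker and stays excluded, so at most 7 return. They carry between 0 and 7 events.

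- Lower limit: 9/(32 + 7) = 9/39 = 23.1%.
- Upper limit: (9 + 7)/39 = 16/39 = 41.0%.

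| Control | Power, 80% reduction kept | Power, treated rate fixed at 5.6% | Largest treated count in 60 with Fisher p < 0.05 |
|---|---|---|---|
| 9/32 | 82% | 82% | 6 (p = 0.037) |
| 9/39 | 77% (treated 4.6%) | 71% | 4 (p = 0.030) |
| 16/39 | 97% (treated 8.2%) | 99% | 13 (p = 0.045) |

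The 80% column follows the plan's own definition of 5.6% as an 80% reduction from 28%. The last column assumes Fisher's test, because the plan names no test.

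**5. Accrual.** Plan: 48 − 16 = 32; 32 × 0.75 = 24 per year; 60/24 = 2.5 years. Outer limit: exclusions 9/48 = 18.8%; 39 × 0.75 = 29.25 per year; 60/29.25 = 2.05 years. This holds only if the section 11 review does not remove the same men.

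**The case against.** The strongest reply is that sections 6 and 11 together already give a common rule. Checking medication lists for interactions with tamsulosin is a documented part of prospective screening, and a list of drugs found on 2019 charts is what a retrospective version of that review would produce. The phrase about high risk for side effects could also be read as open-ended. On that reading both groups are screened on one principle, and the gap is one of documentation. The class mismatch, moreover, rests on pharmacology that the plan does not state.

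Part of this stands. The review may remove the same men, in which case the shift is nil. But nothing ties the list to the review, and a fixed list for one group and a discretionary decision for the other are not the same written rule.

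A reader might infer more than the documents support in two ways.

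- **That the control rate is biased.** The 43.8% among removed men against 28.1% among those kept looks suggestive, but the 16 include the 8 Flomax users, the difference is compatible with chance (p = 0.34), and events are not split by reason.
- **That 23% to 41% is a likely range.** The upper limit needs seven men to return, all with POUR, and no event in any Flomax user. The lower limit needs seven to return with none. Both rates lie inside the confidence interval of 9/32.

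That ten drugs are named for 8 men proves nothing by itself, since a man can take more than one. It does mean the list cannot be read as one drug per man.

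**Conclusion.** The point holds as a gap in assurance: as written, the control can be selected by a different medication rule from the treated group. It does not hold as a demonstrated bias. The number of men affected lies between 0 and 7, and the direction is unknown. The limits in the working are bounds, not estimates; they rest on ordinary drug classes and on the list naming drugs actually seen in 2019.

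The yearly range of 8.3% to 33.3% reported in section 13 is a larger threat to comparability. This one still deserves correction, because it touches the only comparator and several planning figures and is cheap to remove.

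**What to change.** Reconcile sections 6, 11 and 13 into one written medication-eligibility rule. The investigators decide its content without reference to 2019 POUR outcomes by drug, and fix it before any further comparison. Apply it identically to enrolled patients and to all 48 men from 2019, with chart reviewers blind to POUR status.

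Report the 2019 exclusions and POUR events by reason, and restate control n, control rate, exclusion rate, accrual and power. The overall 2019 outcomes are already known, so reopening the selection carries its own risk of an outcome-driven choice. If the control set changes, therefore, also report the comparison against the present 32 men as a sensitivity analysis.

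The cost is a re-screen of 48 charts, a change of wording, and stated figures that may become less favourable.
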